Appendix IV

Karnofsky Physical Condition Score:

This criterion was proposed by Karnofsky of ECOG (Eastern Cooperative Oncology Group). Based on the patient's ability to perform normal activities, their condition, and their level of independence, the KPS recognizes the patient's health status as a total of 100 points, with a 10-point scale. The following table summarizes the criteria. See the table below:

- 1. normal, no signs and symptoms 100 points
- 2. able to perform normal activities with minor signs and symptoms 90 points
- 3. Barely able to perform normal activities with some signs or symptoms 80 points
- 4. Can take care of himself/herself, but cannot maintain normal life and work 70 points
- 5. Can take care of himself/herself mostly, but needs help occasionally 60 points
- 6. Needs care often 50 points
- 7. Cannot take care of himself/herself and needs special care and help 40 points
- 8. Severely unable to take care of themselves 30 points
- 9. Seriously ill and need to be hospitalized for active supportive treatment 20
- 10. Critically ill, close to death 10
- 11. Dead 0

Note: The higher the score, the better the health, the more tolerant of the side effects of treatment on the body, and therefore the more likely to receive complete treatment. The higher the score, the better the health, the more tolerant the treatment is of side effects, and therefore the more likely it is to be complete. The lower the score, the worse the health status, and below 60, many effective anti-tumor treatments cannot be administered. Anti-tumor treatments cannot be given if the score is below 60.

Appendix V

Simplified Appetite Scale (SNAQ)

For each entry in the questionnaire below, please circle the answer you think is correct and score it according to the following numerical intervals: a = 1, b = 2, c = 3, d = 4, e = 5. The sum of the scores for each entry constitutes the Simplified Nutritional Appetite Quotient (SNAQ) value. A value $> \leq 14$ indicates that you are at significant risk of losing at least 5% of your body weight in the next six months.

1. My appetite
 - a. Very bad
 - b. Not good
 - c. Average
 - d. Good
 - e. very good
2. When I eat
 - a. after a few bites, I feel full.
 - b. one-third of the way through, I feel full.
 - c. I feel full after eating half of it.
 - d. I feel full after eating a large portion of it.
 - e. I feel full after eating the majority of my meal.
 - e. I never feel full.
3. When I eat, I feel that the food tastes
 - a. very bad.
 - b. bad.
 - c. good.
 - d. very good.
4. I usually eat
 - a. less than one meal a day.
 - b. Just one meal a day.
 - c. two times a day.
 - d. three times a day.
 - e. Three times a day.
 - e. More than three meals per day.

## Statistical analysis

### 1 Statistical analysis data set

#### ① Full Analysis Set (FAS)

is the ideal set of subjects that is as close as possible to the principle of intentional analysis (the primary analysis is to include all randomized subjects), and which is derived from the smallest and reasonably methodologically sound elimination of all randomized subjects. Estimates of missing values for the primary variables were carried forward (carry-forward) to the point where trial data were missing using the Last Observation Carry Forward (LOCF) method, with the number of subjects evaluating efficacy at endpoint remaining the same for each group as at the start of the trial. the FAS population was used for the analysis of the primary and secondary efficacy measures.

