4.3.2 Self-withdrawal of subjects from the trial

According to the provisions of the informed consent, the subject has the right to withdraw from the trial in the middle of the trial, or the subject has not explicitly proposed to withdraw from the trial, but no longer accept the treatment and testing and lost visits, is also considered to be "withdrawing" (or "shedding"). As far as possible, the reasons for withdrawal should be

understood and documented. Regardless of the reason, a case record form should be kept for cases who drop out of the trial, and a full data set of efficacy and adverse events should be analyzed with the last test result carried forward as the final result.

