5.2 Treatment program

5.2.1 Ear acupuncture group

Ear acupuncture treatment + conventional nutritional support and symptomatic treatment (refer to "Diagnostic and therapeutic path of anorexia nervosa" of tumor nutrition and supportive therapy committee of China Anti-Cancer Association).

Commonly used main points: Shenmen, stomach, spleen, subcortex.

Auxiliary points: Sanjiao, sympathetic, liver, small intestine.

Methods: Embed an earring needle and fix it with adhesive tape, press each point for about 2 minutes each time, 2-3 times a day, the pressure depends on the tolerance of the individual, alternating between the two ears, 2-3 times a week, 4 weeks of treatment, observation until 8 weeks.

5.2.2 Control group: Conventional nutritional support and symptomatic treatment.

During the treatment period, both groups can use supportive therapy reciprocally, if there are treatment-related adverse events, they should be handled separately, and the causes, history, symptoms and treatment measures should be recorded in detail. During the treatment period, both groups of cases could adopt the international standard protocol (Version 3.2014 NCCN) with or without standard chemotherapy or or without standard chemotherapy or radiation therapy.

6 Observation Indicators

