### 2 Statistical analysis plan

Statistical analyses will be calculated using SAS 9.2 statistical analysis software.

The primary validity analysis dataset will be FAS, and PPS will also be analyzed.

All statistical tests will be two-sided, and a p-value of less than or equal to 0.05 will be considered a statistically

The differences tested were considered statistically significant.

Measures for each visit in the different treatment groups were described statistically as mean  $\pm$  standard deviation. Comparisons were made with the baseline values at the time of enrollment using the paired t-test. The paired t-test was used to compare pre- and post-treatment differences within groups. Changes before and after treatment in each group were compared using analysis of variance (ANOVA). The count data of each visit of different treatment groups were statistically described by frequency counts (constitutive ratio). Changes before and after treatment in each group were analyzed using the  $\chi^2$  test or nonparametric The  $\chi^2$  test or non-parametric test was used.

Shedding analysis: The  $\chi^2$  test will be used to compare the total shedding rate and the shedding due to adverse events in each group.

Balanced analysis of baseline values: ANOVA or  $\chi^2$  test will be used to compare demographic data and other baseline indicators to measure how well balanced the two groups are. measure how well the two groups are balanced.

Effectiveness analysis: PPS and FAS were used to analyze the primary and secondary indicators; since this study is a multicenter clinical trial, the impact of central effects on the efficacy indicators should be considered in the analysis. Since this study is a multicenter clinical trial, the influence of center effect on the efficacy indexes should be considered in the analysis.

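### The primary analysis fills missing main-outcome scores by LOCF although needling stops at week 4 and visits run to week 8, which can bias the arm comparison in either direction

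*SAP*

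**What the plan says.** SAP section 1, Full Analysis Set, has missing values of the primary variables "carried forward (carry-forward) to the point where trial data were missing using the Last Observation Carry Forward (LOCF) method". A further clause keeps the denominators fixed, "with the number of subjects evaluating efficacy at endpoint remaining the same for each group as at the start of the trial". This paragraph also describes the set in two ways: "the primary analysis is to include all randomized subjects", and yet it is "derived from the smallest and reasonably methodologically sound elimination of all randomized subjects". SAP section 2 then states: "The primary validity analysis dataset will be FAS, and PPS will also be analyzed". Between-arm comparisons of measured outcomes are by ANOVA on change from baseline.

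Protocol section 4.3.2 repeats the rule for withdrawals, who are analysed "with the last test result carried forward as the final result".

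On timing, protocol section 5.2.1 specifies "4 weeks of treatment, observation until 8 weeks". Sections 6.5.2 and 6.5.3 collect the outcomes at weeks 2, 4 and 8. Section 6.3 lists two main outcomes, the symptom-based anorexia form (Appendix I) and the SNAQ (Appendix V). Neither document names a primary visit.

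No other missing-data method appears in the text available. Dropout rates are compared between arms by chi-square, which describes loss but does not correct for it.

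**The concern.** LOCF assumes that a patient's score would not have changed after the last visit attended. That is doubtful here for two reasons: treatment stops halfway through follow-up, and patients have stage III-IV cancer, with death listed as a discontinuation reason in protocol section 4.3.3.

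At week 8 the direction of the bias depends on facts the documents do not give:

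- It favours needling if the effect fades after week 4, or if appetite declines and needling loses more patients.
- It goes against needling if the losses are reversed, or if patients improve and needling loses more.
- It is about zero if loss and unobserved change balance between arms.

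Patients with no post-baseline visit are a further ambiguity. The constant-number clause implies that they stay in with zero change, while the elimination clause could remove them.

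The per-protocol analysis is no check on LOCF, because it selects adherent patients with completed case report forms. What is at stake is mainly the estimate: a lost effect can look partly sustained, or a null comparison can be tilted.

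**Working it through.** **What can be reproduced.** Only 2 x 30 = 60. The plan gives no effect size, SD, power or dropout rate. For scale, 30 per arm gives 80% power at two-sided 0.05 for (1.960 + 0.842) x sqrt(2/30) = 0.72 SD.

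**Formula.** With higher scores better, LOCF bias at week 8 is, needling minus control, the sum over last-attended visits of (fraction lost there) x (mean at that visit - mean at week 8).

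**In SD units (assumed inputs).** With 20% loss per arm, needling patients falling 0.5 SD after their last visit and controls flat, the bias is 0.2 x 0.5 - 0.2 x 0 = +0.10 SD, about one seventh of 0.72. If both arms worsen by 0.5 SD and loss is 30% needling v 10% control, it is 0.3 x 0.5 - 0.1 x 0.5 = +0.10 SD. With those losses reversed it is -0.10 SD. With equal loss and equal change it is 0.

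**On the Appendix I score.** Twelve items scored 0-4 give a range of 0-48. Assumed: 30 per arm, SD 7, correlation 0.6 between visits, random dropout, two-sample test on change. Spread means that one third of losses each have their last score at baseline, week 2 and week 4. Early means all losses before week 2; late means all after week 4. Rejection rates come from 80,000 simulated trials per main scenario and 20,000 for side checks. With complete data and no effect, rejection was 5.0-5.2%.

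1. *Effect of 2, 4, 0 points at weeks 2, 4, 8, equal loss.* Spread at 30%: 0.1 x (0 + 2 + 4) = 0.6. Late at 30%: 0.3 x 4 = 1.2.

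| Loss per arm | Spread: bias (rejection) | Late: bias (rejection) |
|---|---|---|
| 10% | 0.2 (5.2%) | 0.4 (5.7%) |
| 20% | 0.4 (5.7%) | 0.8 (7.7%) |
| 30% | 0.6 (6.7%) | 1.2 (11.1%) |

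Correlations of 0.4-0.8 leave the bias unchanged; rejection at 30% is then 6.1-8.2% (spread) or 8.7-16.6% (late).

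2. *No effect, 4-point decline in equal steps, unequal loss.* The carried score exceeds week 8 by 4, 8/3 and 4/3 points from baseline, week 2 and week 4, which sum to 8. Spread at 30% v 10%: (0.30/3 - 0.10/3) x 8 = 0.53.

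| Loss, needling v control | Spread | Early | Late |
|---|---|---|---|
| 30% v 10% | +0.5 (6.2%) | +0.8 (8.4%) | +0.3 (5.3%) |
| 20% v 10% | +0.3 | +0.4 | +0.1 |

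Rejection in the second row is 5.0-5.7%. Reversing 30% v 10% reverses the sign.

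3. *Persistent 4-point effect, equal loss 10/20/30%.* Estimated as 3.9/3.7/3.6 (spread), 3.6/3.2/2.8 (early, patients kept with zero change) or 4.0 (late). Spread at 30%: 4 - 0.1 x 4 = 3.6.

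**If baseline-only patients are removed instead.** Scenario 1 spread becomes 0.2/0.4/0.7; for example, 0.6/0.9 = 0.7 at 30%. Scenario 2 at 30% v 10% becomes +0.3 spread and 0 early. The dilution in scenario 3 disappears.

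**Zero-bias cases.** Equal loss with equal decline gives 0. So does an effect of 2, 4, 2 points with equal spread loss: (0 - 2) + (2 - 2) + (4 - 2) = 0.

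**If week 4 is the analysed visit.** Scenario 3 spread still gives 3.9/3.7/3.6. With no effect, a 2- or 4-point decline by week 4 and 30% v 10% spread loss, the bias is +0.2 or +0.4 (5.4%, 5.9%).

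**SNAQ.** Assumed SD 3 and a 1-point effect gone by week 8, equal loss 10/20/30%: bias 0.05/0.10/0.15 spread (5.1-5.5%) and 0.1/0.2/0.3 late (5.2/5.9/6.8%).

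**The alternative.** In the same random-dropout settings a repeated-measures model with constrained baseline had bias within 0.02 and rejection of 4.4-4.9% under no effect.

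**Outcome-related loss.** Suppose there is no other effect and lost patients are 6 points lower at week 8. Loss of 20% v 10% or 30% v 10% gives a true difference of -6 x 0.1 = -0.6 or -6 x 0.2 = -1.2. LOCF and the mixed model both give about 0 with spread or late loss.

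**The case against.** The strongest reply has four parts.

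- **Week 8 may not be the main comparison.** The SAP compares arms on change before and after treatment, and treatment lasts 4 weeks. On that reading the off-treatment problem disappears and the tilts are small. This stands as a limit, but the SAP also describes every visit, so the text does not settle it. At week 4 LOCF would still carry baseline or week-2 scores.
- **The damage is small outside one corner.** The 11.1% figure needs an effect wholly gone by week 8, 30% loss, all of it after week 4, and week 8 as the analysed visit. With spread loss the rejection rate is at most 6.7% under the base assumptions. This is correct, and it limits the severity.
- **Total error does not always favour the mixed model.** At 30% spread loss, root-mean-square error for the SAP's LOCF v the mixed model is 1.67 v 1.75 in scenario 1 and 1.61 v 1.74 in scenario 3. Baseline-adjusted LOCF did better than the mixed model in every spread case run (1.44-1.54 v 1.52-1.75). The mixed model wins clearly for late fading loss of 20% and 30% (1.62 and 1.69 v 1.84 and 2.02). These figures stand. They describe a trade of variance against a bias of unknown sign, and they do not remove the bias.
- **Neither method handles outcome-related loss.** This also stands, and it is why the change of model alone is not enough.

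It can also be argued that, for 60 exploratory patients, a mixed-model or multiple-imputation sensitivity analysis beside LOCF would do. That would be an improvement, but it leaves the headline estimate resting on the no-change assumption.

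**Conclusion.** The concern holds. LOCF is the stated rule for the primary set, needling ends at week 4 with visits to week 8, and the per-protocol analysis does not test the rule. The sign and size of the bias cannot be derived from the documents. Under the assumed inputs for the Appendix I score, it ranges from nothing, when loss and change balance, to about 1.2 points for a lost effect with 30% late loss. A persistent 4-point effect can be diluted to 2.8 if 30% are lost before week 2 and kept with zero change. At 10% equal loss the effect on the test is negligible. Since the trial is described as exploratory, the harm is a misleading estimate more than a wrong confirmatory decision. The change should be made, but the defect does not invalidate the trial. Confidence is medium, because every magnitude rests on assumed dropout, trend, SD and correlation.

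**What to change.** In SAP section 1, Full Analysis Set, make the primary analysis of each main outcome a likelihood-based repeated-measures model on observed scores, without LOCF. Treat baseline as an outcome visit alongside weeks 2, 4 and 8, constrain baseline means equal between arms, and use unstructured covariance. Patients with only a baseline score then remain in the set, in line with its stated aim, although they add no information on the arm contrast. Keep LOCF as a sensitivity analysis and say there how such patients are handled. In protocol section 4.3.2, delete only the carry-forward clause.

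It is also worth naming the visit for the primary contrast and reporting deaths by arm. Add one sensitivity analysis ranking deaths worst and one delta-adjusted analysis, with the delta chosen in advance, because the new model does not cover outcome-related loss.

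The cost is wording in two places and a little programming, with no new visits. No power gain is claimed. With spread loss of 10/20/30% the SD of the estimate is 1.53/1.62/1.73 for the mixed model, 1.59/1.57/1.55 for LOCF as in the SAP, and 1.44/1.43/1.42 for baseline-adjusted LOCF. Against the last, intervals are about 6/13/22% wider (1.53/1.44, 1.62/1.43, 1.73/1.42). Power for a persistent 4-point effect is 72/66/60%, against 75/73/71% for baseline-adjusted LOCF and 66/65/63% for the SAP's unadjusted LOCF.

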#### ② Per Protocol Set (PPS)

Per Protocol Set (PPS): All cases that comply with the trial protocol, use 80%-120% of the medication, have good adherence, do not use banned drugs during the trial, and complete the CRF requirements. The PPS cohort is used for the analysis of primary and secondary efficacy indicators.

#### (iii) Safety Set (SS)

The safety set (SS) is a randomized group of patients who have used the study drug at least once and have at least 1 follow-up visit. The safety set is the main population for the safety evaluation of this study.

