7.3 Judgment of causality with drugs

Indicators of causal judgment for adverse event determination:

- Whether there is a reasonable sequential relationship between the time of initiation of the drug and the appearance of the suspected adverse event;
- Whether the suspected adverse event is consistent with the types of adverse events known for the drug;
- Whether the suspected adverse event can be explained by the effects of the combined drug, the patient's clinical condition, or the effects of other therapies;
- Whether the suspected adverse event resolved or abated after discontinuation or dosage reduction;
- Whether the same reaction recurred after re-exposure to the suspected drug.

Criteria for determining causality: based on the order of the above 5 judgment indicators

Judgment results	Judgment Indicators				
	1	2	3	4	5
Definitely relevant	+	+	--	+	+
Possibly related	+	+	--	+	?

Uncertain	+	+	±	±	?
Possibly not related	+	--	±	±	?
Definitely not	--	--	+	--	--

Explanation: + Affirmative, - Negative, ± Difficult to affirm or deny, ? Circumstances unknown. Based on the table above, determine the relationship between the following 5 levels of adverse events and drugs

- Definitely related, 2 - possibly related, 3 - unable to determine, 4 - possibly unrelated, 5 - definitely unrelated.

The incidence of adverse events was calculated using the total number of cases 1+2+3 as the numerator and all the enrolled cases available for adverse event evaluation as the denominator.

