Safety analysis: the X test was used to compare the incidence of adverse events in the two groups, and the adverse events occurred in this trial were described in a list. Adverse events: the X test was used to compare the incidence of adverse events in the two groups, and the adverse events occurred in this trial were described in a list; the changes of normal/abnormal laboratory test results before and after the trial were analyzed, as well as the relationship between the abnormal changes and the test drug. Safety analysis: The X test was used to compare the incidence of adverse events in the two groups and to describe the adverse events in this trial.

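### The safety set and adverse event incidence are tied to a study drug that neither arm receives, and Protocol 7.3's related-event definition, if carried into the SAP's two-group test, is not like-for-like

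*SAP*

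**What the plan says.** - **Treatments (Protocol 5.2).** The needle arm has ear needling added to usual care. The other arm is described as "Control group: Conventional nutritional support and symptomatic treatment". No study drug, placebo or sham is named. Each arm has 30 patients.
- **Safety population (SAP 1 (iii)).** Randomised patients "who have used the study drug at least once and have at least 1 follow-up visit". This set is the main one for the safety evaluation.
- **Causality (Protocol 7.3).** The first two of five indicators are "Whether there is a reasonable sequential relationship between the time of initiation of the drug and the appearance of the suspected adverse event" and "Whether the suspected adverse event is consistent with the types of adverse events known for the drug". The assessor then uses a table to "determine the relationship between the following 5 levels of adverse events and drugs".
- **Incidence (Protocol 7.3).** "The incidence of adverse events was calculated using the total number of cases 1+2+3 as the numerator", with "all the enrolled cases available for adverse event evaluation as the denominator". Grade 3 is the undetermined category.
- **Test (SAP 2, safety paragraph).** A chi-square "test was used to compare the incidence of adverse events in the two groups". The paragraph does not mention causality grades. It adds a listing of adverse events and a laboratory analysis that again refers to a test drug.
- **Provisions that help.** Protocol 7.1 and 7.4 require adverse events to be recorded and followed, without limiting this to one arm. Protocol 4.3.2 keeps a case record for dropouts and includes their adverse events in the analysis. SAP 2 compares dropout due to adverse events between arms.

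**The concern.** The SAP plans one between-arm test of adverse event incidence. Its population and its numerator both depend on what staff take *drug* to mean, and nothing in the text available says whether it means needling or allocated treatment. Replacing the word would repair the drug condition in the safety set. It would not repair Protocol 7.3, where incidence is limited to events attributed to a treatment, and the two arms do not have the same treatment to attribute to. A comparison built that way can show a difference that reflects the grading rule and not the patients' experience.

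A second, smaller issue is the follow-up visit condition. Protocol 4.3.4 allows a patient to leave at any time for skin irritation or local pain that cannot be tolerated. Those are reactions one would expect mainly with needling. A patient who leaves that way before any follow-up visit would drop out of the main safety population.

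**Working it through.** The plan gives no adverse event rate or derived safety figure, so there is nothing to reproduce. The check applies each reading of *drug* to both arms.

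**Step 1. Who enters the safety set** (30 per arm, before the visit condition)

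| Reading of *study drug* | Needle | Control |
|---|---|---|
| Literal | 0 | 0 |
| Ear needling | 30 | 0 |
| Allocated treatment | 30 | 30 |

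On the second row a two-group test cannot be run within the safety set. Only the third row supports one.

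**Step 2. What enters the numerator.** The first two indicators in the Protocol 7.3 table:

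| Grade | Indicator 1 (timing) | Indicator 2 (known type) | Counted? |
|---|---|---|---|
| 1 | + | + | yes |
| 2 | + | + | yes |
| 3 | + | + | yes |
| 4 | + | -- | no |
| 5 | -- | -- | no |

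Every counted grade needs + on indicator 1. Under the needling reading a control patient has no start time, so on strict use of the table no control event is counted. Under the allocated-treatment reading control events can be counted, but they are judged against care alone, while needle-arm events are judged against needling plus care.

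**Step 3. Illustration of the strict needling reading on the 7.3 denominator.** Counts are assumed. For a v b events with 30 per arm and m = a + b, the uncorrected chi-square is 60(a − b)² / [m(60 − m)]. With b = 0 and a = k this is 60k/(60 − k).

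| k/30 v 0/30 | Chi-square | p, uncorrected | p, Fisher | Expected events per arm (k/2) |
|---|---|---|---|---|
| 3 | 180/57 = 3.16 | 0.076 | 0.24 | 1.5 |
| 4 | 240/56 = 4.29 | 0.038 | 0.11 | 2 |
| 5 | 300/55 = 5.45 | 0.020 | 0.052 | 2.5 |
| 6 | 360/54 = 6.67 | 0.010 | 0.024 | 3 |

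The expected event counts are all below 5, and the SAP does not say whether the chi-square is continuity-corrected.

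**Step 4. Visit condition.** Suppose, as an assumption, that 6 of 30 needle patients have an event (20%) and 1, 2 or 3 of those 6 leave with no qualifying visit. The safety set then shows 5/29 = 17.2%, 4/28 = 14.3% or 3/27 = 11.1%.

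**Step 5. The all-cause comparison.** With equal true rates of 5%, 10%, 20%, 30% and 40% (assumed), the uncorrected chi-square has exact size 2.8%, 5.4%, 4.9%, 4.9% and 4.9%, close to the nominal 5%. Its weakness is sensitivity. With 4 extra needle patients on an equal background, the Step 3 formula becomes 960/[m(60 − m)]:

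| Needle v control | m | Chi-square | p, uncorrected |
|---|---|---|---|
| 7 v 3 | 10 | 1.92 | 0.17 |
| 10 v 6 | 16 | 1.36 | 0.24 |
| 13 v 9 | 22 | 1.15 | 0.28 |
| 16 v 12 | 28 | 1.07 | 0.30 |
| 19 v 15 | 34 | 1.09 | 0.30 |

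**The case against.** The best defence is that *drug* is template wording, that any analyst would read it as allocated treatment, and that the SAP's safety paragraph means all adverse events, since it never mentions grades. Much of this stands. Read alone, that paragraph is a like-for-like comparison. A reader might therefore go too far in inferring that no reading of the plan compares the same quantity in both arms. What the documents show is a conflict: Protocol 7.3 holds their only definition of adverse event incidence, and it depends on attribution.

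A reader might also infer that control incidence is zero by construction. That needs both the needling reading and strict use of the table. A control event does not clearly fit the lowest row either, because that row needs negative answers on stopping and re-exposure, which do not apply. An assessor could call such an event undetermined, and grade 3 is counted. Control grading is then undefined rather than fixed at zero.

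It can also be said that differing attribution is inherent in any related-event comparison of an add-on with usual care. That is true, and it is a reason to compare all-cause events. The two denominators may describe the same people under the allocated-treatment reading, but nothing in the plan says they must.

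Finally, the visit loss is possible but not shown. The SAP does not say that the visit must be a scheduled one, and Protocol 4.3.2 and 7.4 and the dropout comparison reduce the risk.

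**Conclusion.** The point holds as a conflict of definitions that should be reconciled. The safety population and the incidence measure refer to a drug that the trial does not give. If Protocol 7.3 governs the two-group test, the numerator differs in kind between the arms: strictly read as needling, control events go uncounted; read as allocated treatment, the arms are judged against different treatments, with no blinding described. The second reading is the more workable and leaves the smaller defect.

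Only the membership counts in Step 1 follow from the documents. The p-values in Step 3 rest on assumed counts under the less workable reading, and the percentages in Step 4 on assumed departures. Neither is an estimate of what will happen, and the true size of any distortion is unknown. The scope is limited too: this is an exploratory trial of 60 patients, the recorded adverse events are not lost, and the primary efficacy analysis on the full analysis set is untouched.

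**What to change.** 1. Use one safety population in Protocol 7.3 and the SAP: all randomised patients, grouped by treatment received, with no follow-up visit condition. Report by arm how many have no post-baseline adverse event information.
2. Make the between-arm comparison the incidence of all adverse events regardless of attribution, using Fisher's exact test when expected counts are below 5.
3. Reword the causality grading as relation to ear needling, and report events graded 1 to 3 descriptively in the needle arm only.

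The cost is wording in Protocol 7.3 and SAP sections 1 and 2, and slightly more analysis. The statistical price is lower sensitivity to a few local reactions: the scenarios in Step 5 reach only p = 0.17 to 0.30. The descriptive needle-arm report is therefore needed beside the test.

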4.3.4 Disengagement measures and criteria

The investigator should assess the health status and progress of the subject during the treatment period, and the subject can be discharged from the study at any time when the following conditions occur

When the following conditions occur, the subject can be withdrawn from the experiment at any time, and the investigator should provide symptomatic treatment.

- ① When the subject experiences intolerable skin irritation or localized pain;
- ② Decrease of more than 40 points per week in the Kahl score.
- ③ Weight loss of more than 30% per week.

5 Implementation of the program

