6.5.2 Data collection at 2 weeks and 4 weeks of enrollment

Medical record collection: symptom-based anorexia assessment form, simplified appetite scale, fatigue symptom scale, appetite level, body weight, and Kahn's score according to the CRF form.

Therapeutic use of medications

TCM evidence: identify according to TCM identification criteria, check on the CRF form;

Vital signs, physical examination;

blood, urine, stool routine, liver function, kidney function (within 2 weeks);

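### The SAP's safety set requires a follow-up visit, so a needling patient who leaves before week 2 because of a needle-site reaction may be missing from the adverse event incidence, contrary to the protocol's own denominator

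*SAP*

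**What the plan says.** SAP section 1 (iii) defines the safety set as randomised patients who "have used the study drug at least once and have at least 1 follow-up visit", and adds: "The safety set is the main population for the safety evaluation of this study". Both conditions must hold.

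The protocol bears on this in four places:

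- **Visit schedule.** After the pre-enrolment assessment, the first follow-up time point is the one headed "Data collection at 2 weeks and 4 weeks of enrollment" (section 6.5.2). Week 8 follows in section 6.5.3. No early-withdrawal visit is scheduled.
- **Leaving because of a local reaction.** Section 4.3.4 states that "the subject can be withdrawn from the experiment at any time" under listed conditions, the first being "When the subject experiences intolerable skin irritation or localized pain".
- **Incidence of adverse events.** Section 7.3 counts events graded definitely related, possibly related or undetermined, with "all the enrolled cases available for adverse event evaluation as the denominator". It sets no visit condition.
- **Patients who drop out.** Section 4.3.2 says that for such cases "a full data set of efficacy and adverse events should be analyzed with the last test result carried forward as the final result".

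SAP section 2 compares adverse event incidence between the groups by a chi-square test and lists the adverse events. Under its dropout analysis it also compares dropout due to adverse events.

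**The concern.** A safety set should depend on exposure, not on what happened after exposure. Here membership also depends on staying long enough to attend a follow-up visit, and one foreseen reason for not staying is the harm that the safety analysis is meant to measure. A needling patient with a severe local reaction in the first two weeks was exposed and had the event. On the natural reading of the schedule, that patient has no follow-up visit and is removed from both numerator and denominator.

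Controls receive no needle, so needle-site reactions arise in one arm only and no matching loss in control can offset this. With 30 patients per group, one or two such exclusions change the reported rate visibly. The protocol's background already describes the technique as safe, so its local tolerability should be estimated from everyone who was needled.

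The problem is separate from the SAP's reference to a study drug in a trial that has none. Replacing that term by needling would leave the visit condition in place.

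**Working it through.** The documents give no adverse event rate, early dropout rate or safety sample-size figure, so there is no stated figure to reproduce. The check has a textual part and an illustrative part.

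**Text**

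1. First follow-up after enrolment: week 2 (Protocol 6.5.2).
2. Needling frequency: 2 to 3 times a week (Protocol 5.2.1). Sessions up to week 2: 2 × 2 = 4 to 3 × 2 = 6.
3. Withdrawal for a local reaction is possible at any time (Protocol 4.3.4), hence within that window.
4. A patient withdrawn in that window has been needled but has had none of the scheduled follow-ups, and so fails the second condition of the safety set.
5. The same patient, with a recorded reaction, is on the face of it available for adverse event evaluation and belongs in the section 7.3 denominator.

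Steps 4 and 5 give different answers for the same patient, and the SAP does not say which governs.

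**Size, on assumed counts**

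Let a be the needling patients out of 30 (Protocol 1 and 2) with the event, k those of them who leave before the first follow-up, and m the patients who leave that early without the event.

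- All needled patients counted: a/30.
- Safety set as written: (a − k)/(30 − k − m).

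With m = 0:

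| a | a/30 | k = 1 | k = 2 | k = 3 |
|---|---|---|---|---|
| 3 | 10.0% | 2/29 = 6.9% | 1/28 = 3.6% | 0/27 = 0% |
| 5 | 16.7% | 4/29 = 13.8% | 3/28 = 10.7% | 2/27 = 7.4% |
| 8 | 26.7% | 7/29 = 24.1% | 6/28 = 21.4% | 5/27 = 18.5% |

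The first such leaver lowers the rate by 2.5 points (a = 8) to 3.1 points (a = 3). Three lower it by 8.1 to 10.0 points.

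**Direction**

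The reported rate is too low when (a − k)/(30 − k − m) < a/30. This rearranges to k/(k + m) > a/30: the event must be more common among early leavers than in the arm as a whole.

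- *Needle-site reactions.* Some patients leave because of the reaction, so the condition is easily met. With a = 3 and k = 1 it is 1/(1 + m) > 0.10, that is m < 9. Nine event-free early leavers would be needed to bring the rate back to 2/20 = 10.0%.
- *All adverse events.* The condition need not hold. With a = 3, k = 0 and m = 3, 10.0% becomes 3/27 = 11.1%, which is too high. The control arm can lose events too. Suppose each arm has 6/30 = 20.0%, with one needling patient and two controls leaving early with events. The rates become 5/29 = 17.2% and 4/28 = 14.3%, and a true difference of zero appears as 3.0 points against needling.

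**The case against.** The strongest reply is that the protocol already protects these patients. Section 7.3 has the only explicit definition of the incidence, and it requires no visit. SAP section 2 names no population for its chi-square test, so the exclusion follows only from the SAP calling the safety set its main safety population. This stands: what is shown is an unreconciled conflict between the documents, not a certain loss. Section 4.3.2 is weaker support than section 7.3, because it sits under self-withdrawal and its wording is rough.

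Second, the SAP does not define a follow-up visit. A needling session, or the contact at which a withdrawn patient is treated, might be counted as one. Section 6.5 uses follow-up for the scheduled data collections, so week 2 is the more natural reading, but the looser one cannot be ruled out. If it was intended, the condition does little and can be deleted without loss.

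A reader might also go further than the documents allow:

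- *That the event disappears from the report.* It does not. It would still be in the adverse event listing and in the comparison of dropout due to adverse events, and the protocol requires every event to be recorded (7.1) and followed up (7.4). These do not repair the incidence, but they limit the loss to that rate and its test.
- *That the whole safety comparison is biased in favour of needling.* The rule also removes event-free early leavers, and controls who leave early with events. Both arms have stage III or IV disease and may receive chemotherapy or radiotherapy, so control events are to be expected.
- *That the chi-square result would change.* It can in constructed cases: 4/30 against 0/30 gives p = 0.038, and 3/29 against 0/30 gives p = 0.071 (uncorrected). These assume no adverse event of any kind in control, which nothing in the documents supports.

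**Conclusion.** The concern holds in a limited form. Followed as written, the SAP can exclude from its main safety population a patient who was needled, had a local reaction and left before week 2. That conflicts with the protocol's incidence denominator and with its intention to analyse the adverse events of those who drop out.

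For needle-site reactions, excluding these patients understates incidence by roughly 3 percentage points per patient at 30 per arm (assumed example: 10.0% becomes 6.9%). For overall adverse event incidence the net direction is not known.

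The size rests on assumed counts, since the documents give no adverse event or early dropout rate. The exclusion itself rests on reading a follow-up visit as a scheduled one. In a 60-patient exploratory trial this should be corrected because the correction is simple and removes a selection that depends on the outcome. It is not a ground for saying that the safety comparison as a whole favours needling.

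**What to change.** In SAP section 1 (iii), delete the condition that a patient must have had a follow-up visit, and align the definition with protocol sections 7.3 and 4.3.2. Use parallel entry rules for the two arms:

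- needling arm: patients with at least one needle placed;
- control arm: patients who started their allocated conventional care;
- in both arms, whether or not a scheduled visit took place, counting adverse events recorded at any contact up to and including withdrawal.

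The control rule should rest on starting care rather than on randomisation alone. Otherwise a control who starts nothing and is never seen again would count as event-free and lower the control rate. State in SAP section 2 that the chi-square comparison uses this set, and report needle-site reactions separately from other adverse events.

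The cost is a small edit to the SAP. No new data are needed, because adverse events are already recorded throughout the study. There are two small downsides, both to be stated next to the safety table. Early leavers are observed for a shorter time. Needling patients also have more contacts at which an event can be noted: 2 to 3 sessions a week for 4 weeks is 8 to 12 contacts that controls do not have. Separate reporting of needle-site reactions keeps that unequal ascertainment from clouding the comparison of other events.
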